9. Valve hemodynamics (PPM, PPG, MPG; DVI, EOA, LVOT, AI, PVL, EROA) assessed by site-reported echocardiographic parameters preoperatively, at discharge, between 1-3 month, 1 year, 3 year and 5 year.
10. Valve hemodynamics (PPM, PPG, MPG, DVI, EOA, LVOT, AI, PVL, EROA) in a reduced cohort of patients assessed by core lab echocardiographic parameters preoperatively, at discharge, between 1-3 month, 1 year, 3 year and 5 year.

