8.5.9 SUB STUDIES

CT-scan

The collection of the data with the preoperative CT-scan for surgical planning will allow a direct comparison of the measurement done using this imaging system and the measurement done with dedicated valve sizers. Once the aorta of the subject is exposed, the aortic annulus is measured by a standard universal sizers (e.g. Hegar dilator) and the valve's specific sizers. These measurements will allow assessment of the concordance of the aortic annulus size determined by CT-scan with the valve size implanted; and allow a comparison of hemodynamic parameters based on the true annulus size independent of the prosthetic size.

Echocardiography sub-study (Participating Centers Only)

In addition to the echo parameters collected for all the subjects, one fourth (approximately 300 patients) of the trial population will have a complete echocardiographic examination that will be sent to a Core Lab for independent evaluation of the hemodynamic performance in the two treatment groups. At selected centers all patients will be recruited with the agreement to perform the echocardiographic assessment as required by the study guidelines.

The MedStar Health Research Institute, located at MedStar Washington Hospital Center, Washington D.C., USA will serve as the echo Core Laboratory for this clinical trial. [name] and [name] will serve as the Core Laboratory principal investigators.

For this subgroup of subjects the echocardiographic examination is planned at hospital discharge, at the 1-3 month visit, and at the 1, 3 and 5 years visits.

The Core lab may request for the submission of a test echo performed according to the TTE protocol to verify completeness and ensure compatibility, readability prior to enrolling the first subject.

Each postoperative TTE should include all the views and measurements specified on the Site Echo Case Report Form and the echocardiographic protocol (Appendix 5). A copy of the examination will be recorded and will be sent to the Echo Core Laboratory.

The Core Lab will conduct a full analysis of the acquisitions and perform the required analysis, following a completed Core Lab CRF, and send the results to the Sponsor. The Core Lab will discuss any discrepancies or data quality problems through the Sponsor with the clinical site as necessary.

Pacemaker evaluation

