- Echocardiographic examination (TTE) measured at investigational site (MPG; PPG, EOA, DVI, PVL)
- Serious adverse events (as reported in section 17) including all hospitalizations

1 year FUP visit

This visit is for the evaluation of the primary endpoint and is intended to be done as a clinic visit at 1 year \pm 1 month after the day of the surgery. Follow-up evaluations are to be conducted in an office, hospital or clinic setting and are to be performed by the Principal Investigator or designee. If the subject has been seen at another health care facility, the site is to make every effort to obtain the data required for the trial (including copies of source documents) from the subject's offsite physician. All efforts should be made to ensure that the subject comes to the outpatient clinic.

The following data listed below are to be collected:

- Subject status (including NYHA functional classification)
- Physical evaluation
- Medications

- 12-lead electrocardiogram (ECG)
- Modified Rankin Scale and NIHSS assessments
- Blood sample (including WBC, RBC, hemoglobin, hematocrit, platelet count, serum LDH, haptoglobin, reticulocyte, plasma free hemoglobin, serum creatinine and coagulation data)
- Questionnaire for quality of life (recommended)
- Echocardiographic examination (TTE) measured at investigational site (MPG; PPG, EOA, DVI, PVL)
- Serious adverse events (as reported in section 17) including all hospitalizations

2 year FUP visit

This visit is intended to be done between 2 years ± 1 month after the day of the surgery. Follow-up evaluations are to be conducted in an office, hospital or clinic setting and are to be performed by the Principal Investigator or designee. If the subject has been seen at another health care facility, the site is to make every effort to obtain the data required for the trial (including copies of source documents) from the subject’s offsite physician. For this visit telephone follow up is acceptable to collect the clinical information.

The following data listed in **Table 5** below are to be collected according to the type of visit:

Table 5 Data to be collected at 2 year visit according to the type of visit.

Data to be collected	Phone call visit	Outpatient visit
Subject status (including NYHA functional classification)	X	X
Medications	X	X
Blood sample (including WBC, RBC, hemoglobin, hematocrit, platelet count, serum LDH, haptoglobin, reticulocyte, plasma free hemoglobin, serum creatinine and coagulation data)		X

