2.3. SAMPLE SIZE CALCULATION

Total sample size for this trial will be adaptively determined through interim analyses. The sample size will be approximately 900, 1050, or 1234 subjects.

The sample size is based on the analysis of primary endpoint (section 10.1) for assessing non-inferiority of Perceval valve arm compared to the control.

Based on CAVALIER experience, propensity score matched studies^{1,4,5,6} and, GARY registry⁷ the freedom from MACCE composite endpoint is expected to be similar for both arms. The original sample size of 1234 patients was based on CAVALIER experience which reported a freedom from MACCE at 1 year equal to 88%. Blinded review of the data for the ongoing current trial (database snapshot December 2017) estimated the pooled one year MACCE-free rate across arms at 91%, showing an overall primary endpoint higher than originally assumed. Due to this reason, 1234 patients may lead to an overpowered study and a smaller sample size may be required to demonstrate study objectives. In

order to adapt the sample size to the real study performance an adaptive design has been included in the study protocol.

Table 1 summarizes the overall operating characteristics of the design over a range of assumptions for the true underlying MACCE-free rate on control ($MACCE_{ctrl}$) and treatment ($MACCE_{PERCEVAL}$). The information provided by the table are:

- Pr(success): it is the proportion of simulated trials achieving success at the final analysis.
 - when the true effect is exactly at the non-inferiority margin (-0.05), it represents the Type I error; otherwise
 - Pr(success) is the power.
- E[N]: it represents the mean sample size across simulated trials, reflecting an average over some trials that stop with N = 900, some at N = 1050, and others at N = 1234.

Table 1 : Overall operating characteristics

True MACCE_{ctrl}	True MACCE_{PERCEVAL}	True Effect	Pr(success)	E[N]
0.88	0.83	-0.05	0.025	1228.7
	0.88	0.00	0.704	1148.9
0.91	0.86	-0.05	0.023	1228.8
	0.91	0.00	0.805	1128.7

Simulations indicate that the adaptive design is able to control the Type I error and Power of the study while looking for the most appropriate sample size. In fact, under the expected assumption of equivalent arms with 91% MACCE-free rate, the trial has approximately 80% power, the type I error rate is controlled to 2.5% one-side and the average sample size is reduced to approximately 1129.

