2.4. RANDOMIZATION

Subjects are randomly assigned in equal numbers (1:1) to one of two treatment arms:

- Perceval valve
- Standard sutured stented bioprosthetic aortic valve (control)

on the basis of a randomization list that has been performed before study start. Randomization list is stratified by 2 factors:

- country, and
- surgical approach (full sternotomy” or “mini-sternotomy”).

Only subjects who have undergone standard chest CT-scan to determine if the aortic stenosis can be replaced with an available Perceval valve, and is potentially suitable for mini-sternotomy, may be randomized. For each subject the randomization will be performed through eDC system after enrollment and before valve operation, specifically after CT scan and surgical approach (“full sternotomy” or “mini-sternotomy”) has been determined.

One patient will be considered adherent to the randomization if an attempt to implant of the allocated valve is performed. In case of, after an unsuccessful implant, a valve of the other arm is implanted the adherence to randomization allocation will be considered maintained.

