Clinical efficacy (after 30 days)	
Serious Adverse Event (SAE):
 
YES if at least one (Time to SAE >30 days) per CEC or Echo core lab:
 
 - All-cause mortality - All stroke (disabling and nondisabling) - Requiring hospitalizations for valve-related symptoms or worsening congestive heart failure. - NYHA class III or IV (date of assessment >30 days after valve implant) - Valve-related dysfunction: 
 i. (mean aortic valve gradient ≥ 20 mm Hg, EOA ≤ 0.9–1.1 cm² and/or DVI < 0.35 m/s, AND/OR ii. moderate or severe prosthetic valve regurgitation) 
NO, otherwise

Derived variable	Derivation algorithm
Time-related valve safety	
Serious Adverse Event (SAE):
 
YES if at least one (Time to SAE >30 days) per CEC or echo core lab:
 
 - Structural valve deterioration (both points i. and ii. have to be met): 
 i. Valve-related dysfunction: 
 ▪ mean aortic valve gradient ≥ 20 mm Hg, EOA ≤ 0.9(if BSA<1.6 cm²) or 1.1(if BSA≥ 1.6 cm²) cm² and/or DVI<0.35 m/s, AND/OR ▪ moderate or severe prosthetic valve regurgitation) ii. Requiring repeat procedure (TAVI or SAVR) - Prosthetic valve endocarditis - Prosthetic valve thrombosis - Thrombo-embolic event, non-cerebral , - TIA - STROKE - VARC bleeding (BARC type 5, BARC type 3A, 3B and 3C, BARC type 2), unless clearly unrelated to valve therapy (e.g., trauma) : Device and/or procedure related 
NO, otherwise

MACCE (Yes/No)	
Serious Adverse Event (SAE), Valve re-intervention:
 
YES if at least one per CEC:
 
 - Death - Myocardial infarction - Stroke - Reintervention 
NO, otherwise

Derived variable	Derivation algorithm
MACCE @ 1 year (Yes/No)	
Serious Adverse Event (SAE), Valve re-intervention:
 
YES if at least one per CEC:
 
 - Death (Time to SAE <=365 days) - Myocardial infarction (Time to SAE <=365 days) per CEC - Stroke (Time to SAE <=365 days) per CEC - Reintervention (Time to SAE <=365 days) 
NO, otherwise

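### In SAP Table 8, the valve-dysfunction part of Clinical efficacy draws on the CEC or echo core lab only, so echo-only dysfunction outside the roughly 300 core-lab patients is coded NO and the component rate is understated

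*SAP*

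**What the plan says.** SAP section 18.12, Table 8, Clinical efficacy row: the variable is set to "YES if at least one (Time to SAE >30 days) per CEC or Echo core lab" for any listed component, and to NO in every other case. One component is valve-related dysfunction, defined by mean gradient, EOA, DVI or moderate/severe prosthetic regurgitation. Findings count only "per CEC or Echo core lab"; site-read echo is not named as a source, and there is no category for patients who could not be assessed.

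Protocol 8.5.9 (Echocardiography sub-study): "one fourth (approximately 300 patients) of the trial population will have a complete echocardiographic examination that will be sent to a Core Lab". These patients come from selected centers. Protocol 8.5.8, secondary endpoint 10, describes the same data as hemodynamics "in a reduced cohort of patients assessed by core lab echocardiographic parameters".

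Protocol 8.7.1 requires, for every patient, "Echocardiographic examination (TTE) measured at investigational site (MPG; PPG, EOA, DVI, PVL" at discharge, 1–3 months, 1 year, 3 years and 5 years. The core-lab sub-study uses the same visits.

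SAP 13.1.2 computes incidence on all subjects in the group, and on late patients for late events. Table 8 defines late patients by days of exposure, not by having a core-lab echo. No other denominator is given for the VARC-2 composites.

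**The concern.** Clinical efficacy after 30 days is a prespecified secondary endpoint (Protocol 8.5.8, item 5b). A gradient of 20 mmHg or more on a routine echo, without symptoms, need not be reported as a serious adverse event. Outside the core-lab cohort, such a finding has no documented route into the composite. SAP 4.5 describes listings used to screen for CEC adjudicability; they cover cardiac enzymes, ECG, mRS/NIHSS and blood results, but not echo.

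A patient who was never read by the core lab is therefore counted in the same way as one who was read and found normal. The absolute rate is understated and a between-arm difference in valve dysfunction is pulled towards zero.

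The report could also disagree with itself. SAP 8.6 and Table 8 classify site-reported mean gradient at the same 20 mmHg cut, and SAP 11.2.2 analyses leak severity, including moderate/severe, under site-reported echo. Those tables could show many more cases than the composite does.

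**Working it through.** **Inputs from the documents.** Core-lab cohort: about 300, or one fourth (Protocol 8.5.9). Sample size: "The sample size will be approximately 900, 1050, or 1234 subjects" (SAP 2.3). Allocation 1:1 (SAP 2.4).

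**The plan's own figure.** 1234/4 = 308.5, which agrees with about 300. At the earlier stopping points 1050/4 = 262.5 and 900/4 = 225, so one fourth and 300 match only at the maximum N. Taking 300 as fixed, the core-lab share f is 300/1234 = 24.3%, 300/1050 = 28.6% and 300/900 = 33.3%.

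**Model.** Let c be the share of echo-defined dysfunction outside the core-lab cohort that is reported and adjudicated by the CEC. The documents do not give c, so it is ranged from 0 to 1. Assume that every case inside the cohort is captured. Then

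captured share = f + (1−f)c, and observed component rate = true rate × captured share.

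| N | f | c=0 | c=0.25 | c=0.5 | c=1 |
|---|---|---|---|---|---|
| 1234 | 24.3% | 24% | 43% | 62% | 100% |
| 1050 | 28.6% | 29% | 46% | 64% | 100% |
| 900 | 33.3% | 33% | 50% | 67% | 100% |

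Example: N=1234, c=0.25 gives 0.243 + 0.757 × 0.25 = 0.432.

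**Effect on the component.** With assumed true rates of 8% vs 4% (illustrative, not from the documents) and N=1234:

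- c=0: 0.08 × 0.243 = 1.9% vs 0.04 × 0.243 = 1.0%
- c=0.25: 0.08 × 0.432 = 3.5% vs 1.7%
- c=0.5: 0.08 × 0.622 = 5.0% vs 2.5%

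The 4-point difference becomes about 1.0, 1.7 or 2.5 points. At N=900 and c=0 the rates are 2.7% vs 1.3%. If f and c are the same in both arms, the ratio of the two rates is unchanged; only the absolute difference shrinks.

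**Effect on the composite.** Suppose other components give 20% and true dysfunction is 10%, independently (both assumed). The true composite is 1 − 0.80 × 0.90 = 28.0%. At N=1234 the reported figure is 1 − 0.80 × (1 − 0.0243) = 21.9% for c=0 and 1 − 0.80 × (1 − 0.0432) = 23.5% for c=0.25.

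**Time-related valve safety.** This row names the same two sources, but there structural deterioration needs both the echo criterion and a repeat procedure. The CEC adjudicates re-interventions in all patients (Protocol 11.4), so c should be near 1 and little is lost.

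**The case against.** A reader might infer that three quarters of patients cannot meet the echo criterion at all. The documents do not support that. The rule admits either source, structural deterioration and non-structural dysfunction are reportable in every patient up to 5 years (Protocol 17.2), and the CEC includes echocardiography expertise and adjudicates other protocol-defined endpoints (Protocol 11.4). The charter and adjudicability criteria that decide what reaches it are not in the documents. For the same reason 1.9% vs 1.0% is the worst case and not an expected result. A reader might also take both composites to be affected alike; the repeat-procedure condition rules that out.

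Three further points have weight:

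- Valve performance is compared elsewhere. Site-reported hemodynamics in all patients are secondary endpoint 9, and SAP 11.2 analyses gradients and leaks by arm. SAP 13 makes safety summaries descriptive. This limits the damage but does not make the composite right.
- The trial is non-blinded, so preferring independent readers is defensible. That supports showing core-lab results on their own denominator; it does not support counting unread patients as normal.
- The source heading may be loosely drafted, since the same row lists NYHA class, which is assessed at site visits. If so, the row needs correcting anyway, because a programmer following it literally would produce the dilution.

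**Conclusion.** The concern holds for the valve-dysfunction component of Clinical efficacy after 30 days. As written, Table 8 captures between 24% (c=0) and 100% (c=1) of that component at N=1234, and between 33% and 100% at N=900. Even if half the outside cases reached the CEC, more than a third would be lost at N=1234.

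The size depends on c, which is unknown, and on complete capture within the core-lab cohort. Reading the bias as shrinkage towards zero also assumes similar f and c in both arms. The 1:1 allocation makes that plausible for f, though randomization is stratified by country and approach, not by center. In an open trial, event reporting, and hence c, could differ by arm.

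The full composite is affected less than the component. Time-related valve safety is largely unaffected. The primary endpoint, which is CEC-adjudicated MACCE, and the sample size are unaffected. The point merits a correction to a secondary derivation and does not threaten the main conclusion.

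**What to change.** In the Clinical efficacy row of Table 8:

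1. Take the core-lab value where one exists, and otherwise the site-reported MPG, EOA, DVI and regurgitation grade.
2. Report the component in the core-lab subset, with that subset as denominator, as a sensitivity analysis.
3. Code patients with no usable echo and no other qualifying event as not evaluable for this component, not as NO, and show their number by arm.
4. State the source of NYHA class in the same row.

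The cost is a SAP derivation change and some reprogramming; no new data are needed. The downside is that site reads are noisier and made by readers who know the valve, and that sources would differ by center. The core-lab analysis checks this, but only roughly. With about 150 patients per arm and the assumed rates of 8% vs 4%, the standard error of the difference is √(0.08×0.92/150 + 0.04×0.96/150) = 2.7 points, so a 95% interval spans about ±5.4 points. That is why the subset serves better as the sensitivity analysis than as the only source.

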18.12. DATA DERIVATIONS

Table 8 : Data derivation rules

Derived variable	Derivation algorithm
Consented subject	Yes if filled date of consent No, otherwise.
Enrolled subject	Yes if filled date of consent AND patient is not a failure to implant (termination reason= FAILURE TO MEET RANDOMIZATION CRITERIA) No, otherwise.
ITT subject	Yes if Randomization date not empty No, otherwise.
mITT subject	Yes if ITT and the valve is a study valve (as listed in CRF). In case of "other" values, they have to be checked one by one with PM. No, otherwise.
Adherence to Randomization allocation	Yes if "Was the randomized valve implanted?" at first attempt=Yes No, otherwise.
SAF subject	Yes if Randomization and Implant dates not empty No, otherwise.
PP subject	Yes if 
 - Randomization and Implant dates not empty - Adherent to randomization - no major protocol violation (as reported in CRF field). No, otherwise.

Derived variable	Derivation algorithm
Operating room suite time (min)	Implant, Surgical time: Finish time – Start time
Skin-to-skin time (min)	Implant, Surgical time: Finish time – Start time
Extracorporeal circulation time (min)	Implant, Surgical time: Finish time – Start time
Cross clamp time (min)	Implant, Surgical time: Finish time – Start time
ICU stay (minutes)	Intensive Care Unit: [Date/Time of ICU Discharge] - [Date/Time of ICU Admission] If time of ICU discharge is missing it will be set at 23:59 If time of ICU Admission is missing it will be set at 00:00
ICU stay (days)	ICU stay (minutes) / 1440
Time to SAE	Serious Adverse Event (SAE): SAE start date – Surgery date +1
Early, Late SAE	EARLY if Time to SAE ≤ 30 days LATE if Time to SAE > 30 days

Derived variable	Derivation algorithm
Early safety (at 30 days)	
Serious Adverse Event (SAE):
 
YES if at least one (Time to SAE <=30 days) per CEC:
 
 - All-cause mortality - All stroke disabling and nondisabling - Life-threatening bleeding - Acute kidney injury—Stage 2 or 3 (including renal replacement therapy) - Coronary artery obstruction requiring intervention - Major vascular complication - Valve-related dysfunction requiring repeat procedure (BAV, TAVI, or SAVR): SVD and Aortic regurgitation requiring re-intervention 
NO, otherwise

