MACCE @ n year (Yes/No)	
CEC adjudication of Serious Adverse Event (SAE), Valve re-intervention:
 
YES if at least one per CEC:
 
 - Death (Time to SAE <=n*365.25 days) - Myocardial infarction (Time to SAE <= n*365.25 days) per CEC - Stroke (Time to SAE <= n*365.25 days) per CEC - Reintervention (Time to SAE <= n*365.25 days) 
NO, otherwise

PM implant	
SAE FORM – TREATMENT
 
Yes if:
 
 - Was a pulse generator implanted? = YES - If yes, specify = Pacemaker 
NOTE: PM implant will be classified as intraoperative, early or late according to the date of PM implant (not the AE start date)

Derived variable	Derivation algorithm
Last exposure date	
Study Termination, Serious Adverse Event (SAE):
 
 1. For explant of investigational device: date of explant 2. For dead subjects: date of death 3. For alive and not explanted subjects: 
 - Date of termination - If there is no date of termination, the last available FU date (including discharge) or the last SAE date (occurrence date), whichever occurs later. - If there is no follow-up and no adverse events : date of surgery or date of randomization, whichever occurs later.
Last study date	
Study Termination, Serious Adverse Event (SAE):
 
 1. For dead subjects: date of death 2. For alive subjects: 
 - Date of termination - If there is no date of termination, the last available FU date (including discharge) or the last SAE date (occurrence date), whichever occurs later. 
If there is no follow-up and no adverse events : date of surgery or date of randomization, whichever occurs later.

Study length (days)	
Study termination, Subject Information:
 
Last study date – Enroll Date+1

Extent of exposure (days)	
Last exposure date-surgery date+1

Late patients	
Subjects with more than 30 FU days of exposure

Patient-years	
Cumulative Study length (days)/365.25

Derived variable	Derivation algorithm
Early patient-years	Cumulative Study length (days) up to 30 days/365.25
Late patient-years	Cumulative Study length (days) from 31st day/365.25. Subjects with less than 31 FU days do not contribute to the late patient-years

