SAE starting date (missing)	In case of missing SAE starting date, the following rule will be applied: 
 1. If missing day: 1st day of the month 2. If missing day and month: 01-JAN 3. If totally missing: Date of surgery SAE starting date cannot be before the surgery date. In that case, SAE starting date will be set as date of surgery.
Deaths	Death is when there is a SAE: 
 - With outcome='FATAL' OR - Leading to death (SAE criteria) The date of death is retrieved from the SAE form (Date of death).
Leak severity	Leak will be classified in: 
 1. none/trace: if "Is there a Paravalvular Leak?" ("Is there a Central Leak?")='No' or severity=' Trace (<1/4+)' 2. mild: if severity=' Mild (1/4+)' 3. moderate/severe: if severity=' Moderate (2/4+)' or severity=' Severe (>= 3/4+)'

Derived variable	Derivation algorithm
Proportion of patient event-free at one year	For each MACCE component: Numerator: #patients who experienced the specific MACCE component within DAY 365 Denominator: #patients who experienced the specific MACCE component within DAY 365 + # patients without the specific event at DAY 365
Proportion of patient MACCE-free at each year	Numerator: #patients who experienced MACCE within DAY 365 (730, 1095, 1460, 1825) Denominator: #patients who experienced MACCE within DAY 365 (730, 1095, 1460, 1825) + # patients without MACCE at DAY 365 (730, 1095, 1460, 1825)
MPG Gradient class	Aortic Mean Pressure Gradient (MPG) class: 
 • MPG \geq 20mmHG • MPG < 20mmHG
Hospitalization time [days]	Discharge – Hospital Admission +1
Ward time [days]	Hospitalization time – ICU time
EQ-VAS	Use as first source of values the “EQ5D02-Your Health Today” variable. If it’s missing, use the “EQ VAS Score” to replace the missing value.
Aortic Mean Pressure Gradient (MPG) with LVOT adjustment	Aortic Mean Pressure Gradient - LVOT Mean Pressure Gradient
Peak Mean Pressure Gradient (MPG) with LVOT adjustment	Aortic Peak Pressure Gradient - LVOT Peak Pressure Gradient

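### SAP Table 8 times death by the start of the fatal SAE in the MACCE, early-safety and clinical-efficacy rules, in conflict with its own date-of-death rows; the expected effect on the primary endpoint is small

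*SAP*

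**What the plan says.** All of the following are in SAP section 18.12, Table 8, unless stated otherwise.

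- **Time to SAE** is "SAE start date – Surgery date +1".
- **MACCE @ 1 year** includes "Death (Time to SAE <=365 days". **MACCE @ n year** includes "Death (Time to SAE <=n*365.25 days".
- **Early safety** lists all-cause mortality under "YES if at least one (Time to SAE <=30 days) per CEC". **Clinical efficacy** lists it under "YES if at least one (Time to SAE >30 days) per CEC or Echo core lab".
- **Deaths**: a death is an SAE with a fatal outcome or one that led to death, and "The date of death is retrieved from the SAE form (Date of death".
- **Last exposure date** and **Last study date** both use "For dead subjects: date of death".
- **Event-free proportion** rows count patients who had the event by day 365 (or the later yearly cut-offs), without mentioning Time to SAE.
- **PM implant** carries an explicit override: "PM implant will be classified as intraoperative, early or late according to the date of PM implant (not the AE start date".
- **SAE starting date (missing)** replaces a missing day by the first of the month, a missing day and month by 1 January, and a fully missing date by the date of surgery.

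Outside Table 8, SAP section 13.1.2 applies time-to-event methods to the time to onset of deaths. Section 18.10.3 computes time to onset from the date of implant and the imputed AE start date.

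**The concern.** Death has a date of its own, and a death at one year or at 30 days should be decided by that date. Table 8 instead substitutes the onset of the illness that caused it. Three consequences follow if the rows are programmed literally.

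1. A patient alive at the cut-off is counted as dead at the cut-off whenever the fatal SAE had already started.
2. A death after day 30 from an SAE that began by day 30 moves into early safety. It also fails the after-30-days condition, so it drops out of clinical efficacy.
3. A fatal SAE with a fully missing start date is placed on the day of surgery, however late the patient died.

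The displacement is one-way: where the two dates differ, deaths move earlier. It also ties an objective component of the primary endpoint to SAE onset, which needs judgement, in a non-blinded trial. The pacemaker row shows that the SAP writes out an exception to the start date when one is intended. No such exception is written for death.

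**Working it through.** **1. Apply the rule to two dated cases (surgery 2 January 2018).**

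| | SAE start | Time to SAE | Death | Day of death | Result as written |
|---|---|---|---|---|---|
| A | 20 Dec 2018 | 353 | 20 Jan 2019 | 384 | one-year MACCE by death, though alive at day 365 |
| B | 20 Jan 2018 | 19 | 20 Feb 2018 | 50 | early-safety death; not counted as a death in clinical efficacy |

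Under the event-free proportion rows, patient A would most naturally be free of death at day 365. The two parts of Table 8 therefore give different answers for the same patient.

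**2. Reproduce the plan's own figures.** SAP Table 1 gives Pr(success) of 0.805 at 91% event-free in both arms and 0.704 at 88%. Inputs: maximum 1234 enrolled (SAP 2.3), 10% attrition to per protocol (protocol 10.3), 1:1 allocation, margin 0.05, prior Normal(1.99, 3²) on the log-odds, threshold 0.9775 (SAP 10.2-10.3). Per-protocol number: 1234 × 0.90 ≈ 1110, or 555 per arm.

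- Exact binomial enumeration at the fixed maximum size gives 0.817 at 91% and 0.714 at 88%.
- A simulation of the adaptive design (4000 trials; assumed uniform accrual over 30 months, half of events in month 1, normal approximation to the posterior) gives 0.814 and 0.709.
- Type I error at 91% against 86% is 0.0235 (exact); SAP Table 1 states 0.023.

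These agree with the plan closely enough to serve as a baseline.

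**3. Size at one year.** The share of patients with onset by day 365 and death after it is roughly the death hazard times the mean onset-to-death lag. Neither is in the documents. Assume 3-4% per year and 10-30 days:

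- low: 0.03 × 10/365 = 0.08%; × 1110 = 0.9 patients
- high: 0.04 × 30/365 = 0.33%; × 1110 = 3.7 patients

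This is an upper count for the composite. If the fatal SAE is itself an adjudicated stroke, myocardial infarction or re-intervention by day 365, the patient is already a MACCE and only the death component is mistimed.

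**4. Effect on the primary test.** Let q be the share added to events in both arms, starting from 91% by date of death, at 555 per arm:

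| q | Patients per arm | Power | Type I error |
|---|---|---|---|
| 0 | 0 | 0.817 | 0.0235 |
| 0.25% | 1.4 | 0.808 | 0.0235 |
| 0.5% | 2.8 | 0.798 | 0.0236 |
| 1% | 5.5 | 0.780 | 0.0236 |

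The range in step 3 lies between the first and third rows. Only if every displaced death fell in one arm would the test move materially. At q = 0.25%, power would be 0.771 (Perceval only) or type I error 0.032 (control only). These are bounds, not expectations.

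**5. Size at 30 days.** No figure in the documents gives the share of patients who die after day 30 from an SAE that began by day 30, so no calculation is possible.

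**The case against.** The best defence is that the SAP is inconsistent rather than uniformly wrong. The Deaths row gives death its own date, the exposure and study-length rows use it, and the event-free proportion rows, which section 11 relies on for the component and annual analyses, fit it better. A programmer may well have used the date of death. The MACCE and early-safety rows are also decided per CEC, and the CEC charter is not in the documents, so the committee may assign its own death date. This stands as a limit on what can be said about how deaths will actually be timed. It does not cure the text: none of those rows overrides the explicit condition in the MACCE and safety rows.

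Two stronger readings are tempting and are not supported.

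- *A reader might infer that the non-inferiority result is at risk.* The expected count is a handful of patients against a 5-point margin. Balanced displacement leaves type I error unchanged, and nothing in the documents suggests that displacement would differ between arms.
- *A reader might infer that 30-day mortality or early safety is inflated by a stated amount, for example relative to the 3.4% early mortality in protocol section 6.2.* Any such amount would only restate an assumption. That section does not define its early period as 30 days. Many early-onset fatal complications (stroke, life-threatening bleeding, stage 2-3 kidney injury, major vascular complication) already make the early-safety composite positive. That composite is also only summarised descriptively (SAP 13).

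On missing start dates, section 18.10 says replacement of a missing year is not foreseen, so the day-of-surgery displacement applies only where the Table 8 rule governs.

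**Conclusion.** The point holds as a conflict within the SAP that needs resolving. Read literally, Table 8 dates death by SAE onset in four endpoint rules, and sections 13.1.2 and 18.10.3 do the same for the mortality time-to-event analyses, against rows of the same table that use or imply the date of death. The wording is certain; which date would be used in practice is not.

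For the primary endpoint the expected effect is at most about 1-4 of about 1110 patients, resting on the assumed hazard and lag, and fewer where the fatal SAE already qualifies as a MACCE component. Power changes by about one point (0.817 to 0.808 at q = 0.25% in both arms). No effect on the non-inferiority conclusion is demonstrated. The direction at 30 days is clear, with deaths moving into early safety and out of clinical efficacy, but the size is unknown. This is a modest correction, justified because it concerns a primary-endpoint component and costs almost nothing.

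**What to change.** Add a row to SAP Table 8: time to death = date of death − surgery date + 1. Refer to it, in place of Time to SAE, for the death component of MACCE @ 1 year, MACCE @ n year, early safety and clinical efficacy, and for all mortality time-to-event analyses in section 13.1.2. State in section 18.10.3 that deaths are exempt from the onset rule. Keep the SAE start date for the non-fatal components.

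Add a rule for partial or missing death dates, separate from the SAE start-date rule, so that a missing onset date can never place a death on the day of surgery. If the CEC assigns a date of death, say that this is the date used.

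The cost is one derivation row and a few cross-references. The date of death is already on the SAE form, and sample size, margin, prior and posterior threshold are unchanged.
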